Phase I: To create VR-M to focus on virtual reality job interview training for transition-age youth with ASD receiving vocational services. We will solicit feedback on the training tool using mixedmethod semi-structured feedback forms with high school (HS) youth with ASD (n=20) or other educationally defined disabilities (n=10) as well as employed adults with ASD or other prior educational disability as well as parents, employers, and vocational counselors that support youth with ASD, educational disability, or adjudication (n=30) to systematically evaluate the core components of VR (e.g., interview content, virtual character, VR interface, and didactic content). Qualitative interview data will be analyzed for themes regarding technical content-based limitations of VR. SIMmersion will then integrate the qualitative results to create a tailored learning system.

Phase II: To evaluate the feasibility and preliminary effectiveness of VR-M in a randomized pilot trial comparing vocational-services-as-usual with VR-M added on (VSU+VR-M) to VSU only. Transition-age youth with ASD (n=90) will be enrolled in a 6-month trial to test all study protocol

3 of 24

aspects including VR-M training effectiveness, recruitment procedures, and assessment tools. VR-M will be administered at educational programs supporting rural, suburban, and urban youth to capture greater variation in programming and students. We will monitor VR-M treatment fidelity, acceptability, usability, feasibility, and tolerability.

Phase IIa: To assess whether VR-M is associated with enhanced job interview skills (primary target) and interviewing self-confidence, and reduced interviewing anxiety. Compared to VSU, the VSU+VR-M group will improve interview skills (Hyp 1), increase self-confidence (Hyp 2), increase motivation (Hyp 3) and reduce anxiety (Hyp 4).

Phase IIb: To assess whether VR-M is associated with higher employment rates and attaining employment sooner at 6-month follow-up. Compared to VSU, the VSU+VR-M group will: a) have a greater likelihood of attaining employment (Hyp 5) and b) attain employment sooner at 6-month follow-up (Hyp 6).

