These visits should last approximately 60 minutes each. Students will receive a \$25 gift card for each visit. The consent and reading test will always be first, but the following activities may be done in a different order depending on the student availability. We aim to work best within the school and their availability. Study staff will complete the following tasks with student:

- Assent/Consent
- Reading Level: Wide Range Achievement Test (4th Edition) to assess current reading level. (If students do not pass a 3rd grade reading level, participation will end and they will be compensated \$10).
- Cognitive Assessments on an iPad using the National Institute of Health Tool Box
 Application
- Baseline Employment Survey
- Mood Survey
- Job practice interview Role-Play (audio and video recorded)
- Self-Report Surveys about:
 - a. Anxiety
 - b. Motivation
 - c. Self-confidence

D.4. Randomization:

Students will be randomized into the VR-M group or the control group. This will be done at a ratio of 2:1 (VR-M:control). Family and teachers will be informed by research team if student is active in the Intervention group or the Control group. The Control group will continue their educational services as usual and skip "visits" 3-16. They will return for the last in person Study Visit 17. Block randomization

tables will be created prior to the study based on computer generated blocks of four. Blocks of four will ensure nearly equal groups. Envelopes or paper containing the randomization by sequential subject entry number will be created and stored, and then opened when a participant has completed pre-randomization procedures.

D.5. Study Visit 3:

Students randomized to the VR-M group will receive a 45-60 minute orientation to use the Virtual Interview Training program.

D.6. Study Visit 4:

Students will train with the educational content. Study staff will be on site to help troubleshoot and answer questions if needed.

D.7. Study Visit 5:

Students will use one class period for orientation to learn to navigate and participant in the virtual interview.

D.8. Study Visit 6-16:

Students will complete up to 3 virtual job interviews per class period. Teachers will help implement this in their classrooms and may decide to utilize homework for the students where they are assigned to use the tool at home as well as in the school.

D.9. Study Visit 17:

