Minors will participate in this study. A legal guardian will be required to provide parental consent and if the child participates in the study, they will be assented using the most appropriate form for their language and cognitive level. Pregnant women will not be excluded from the study. Their participation will not differ from participants who are not pregnant.

5.0 Multiple Sites:

This is a multi-site project funded by the National Institute of Mental Health and discretionary funding where the Principal Investigator is [name] located at the University of Michigan. He has previously worked directly with teachers at each site where the teachers provided information to families and then directed them to [name] so that he can facilitate the recruitment of students and families into the study to complete the feedback forms, and train local school staff at each study site to administer the intervention.

A. University of Michigan School of Social Work is the coordinating site where all data will be entered, cleaned, stored, and analyzed

- B. Ann Arbor Academy is research site #1. Ann Arbor Academy has students from grade 4-12 with a variety of learning issues including students with autism spectrum disorder as well as other educational/ learning impairments. Their college prep program prepares students for higher education and the workplace. At this site, we will recruit research participants (both minors and adults) to participate in this research study. Although data will be collected at this site, research staff will transfer the collected data in a locked box to the UM research site for processing.
- C. Troy Beaumont Project Search is research site #2. Troy Beaumont Project Search is a business-led program for post high school age students with intellectual and developmental impairments between the ages of 18 and 26. The program is conducted entirely at the workplace where students receive instruction and training in a workplace setting. Although data will be collected at this site, research staff will transfer the collected data in a locked box to the UM research site for processing.

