Phase II emphasizes the evaluation of VR-M training on interviewing skills and attaining employment. We recognize that the heterogeneity of ASD may affect these outcomes. We will assess the effect of VR-M on changes in job interview skills, self-confidence, motivation, and anxiety between pretest and postest. We will determine the likelihood of attaining a job for the two conditions by 6 months, a "real-world" outcome and the issue of greatest concern. The mean number of interviews per week and time-to-employment for the two groups at 6-month follow-up will be examined. Additional analyses will evaluate the mechanisms of VR-M that lead to improved interview performance and positive employment outcomes via mediators (improved self-confidence, improved motivation, reduced anxiety) and moderators (e.g., ASD-related symptoms, depressive symptoms, and neurocognitive function) that might affect responsiveness to VR-M. This data will inform our understanding of how interventions like VR-M affect outcomes. We will use repeated-measures ANCOVAs with ASD-related symptoms, depressive symptoms, neurocognitive function, and social cognitive function (now listed as heterogeneity variables) as covariates. We will also use ANCOVA to evaluate the change over time, with posttest scores as the dependent variables while covarying for pretest variables. Cohen's d effect sizes will characterize the observed differences. We will use a log-rank test comparing time-to-position

in the two groups to determine a hazard ratio to test if time-to-position differs between groups. The effects of covariates, including blocking factors, on time to employment will be assessed using Cox proportional hazards regression⁴⁷.

Exploratory Data

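### Section 14.0 does not say how students who already hold a job at baseline are treated in the employment analyses (Hyp 5 and Hyp 6)

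*Combined protocol and SAP*

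**What the plan says.** - **Hypotheses.** Section 1.0 (Phase IIb) expects the VR-M arm to be more likely to attain employment (Hyp 5) and to do so sooner (Hyp 6).
- **Eligibility.** Section 3.0 requires students to be receiving transition services. No inclusion criterion requires being without work, and neither exclusion criterion concerns employment.
- **Data.** Section 4.0 D.2 lists a "Baseline Employment Survey" at Visits 1 and 2. Under D.4 the allocation is opened only after the pre-randomisation procedures are complete.
- **Analysis of Hyp 5.** Section 14.0 Data Analysis says "We will determine the likelihood of attaining a job for the two conditions by 6 months". It names no model, analysis set or event definition.
- **Analysis of Hyp 6.** Section 14.0 says "We will use a log-rank test comparing time-to-position", with Cox regression for covariates. It gives no time origin and no rule for a job already held. Blocking factors are named among the Cox covariates; baseline employment is not.
- **General covariate rule.** Section 14.0 also tests baseline characteristics between arms and considers as covariates those that differ significantly. This is the only route by which baseline employment could enter.

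**The concern.** A time-to-event analysis needs an event time, or a censoring time, for every student. For a student who has a job at entry, the plan as written allows at least four treatments: an event at time zero, a student who never has the event, a student whose next new job is the event, or exclusion. These give different answers, and nothing prevents the choice from being made after the data are seen.

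Under the first two treatments these students have the same outcome whichever arm they are in, so they pull the arms together. An imbalance between arms in baseline jobs also moves the estimate, and the covariate rule corrects it only when it is large enough to be significant. Section 14.0 ranks employment by 6 months as the outcome that matters most in practice.

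**Working it through.** The plan states no power, alpha, effect size or expected employment rate, so it has no figure of its own to reproduce. What follows is an illustration.

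**Inputs from the documents**
- Section 1.0: "Transition-age youth with ASD (n=90) will be enrolled in a 6-month trial".
- Section 4.0 D.4: 2:1 allocation, hence about 60 VR-M and 30 control students.
- Section 2.0: employment of 6-12% among recent high-school graduates with ASD and 25-50% among individuals with ASD generally. Neither is a baseline share for this trial.

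**Assumptions**
- Among students without a job at baseline, 50% (VR-M) and 25% (control) gain one.
- A share q, equal in both arms, holds a job at baseline.
- Two-sided 5% pooled two-proportion z-test, power by exact binomial enumeration, no loss to follow-up.

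**Three treatments**
- A, a job held counts as attained: rates q + (1−q)·0.50 and q + (1−q)·0.25.
- B, only new jobs count and employed students gain none: rates (1−q)·0.50 and (1−q)·0.25.
- C, employed students removed: rates 0.50 and 0.25 in 60(1−q) and 30(1−q) students, rounded.

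Under both A and B the risk difference is (1−q)·0.25. At q = 20%, A gives 0.60 − 0.40 = 0.20 and B gives 0.40 − 0.20 = 0.20.

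| q | Risk difference, A or B (points) | Power A | Power B | Power C (n) |
|---|---|---|---|---|
| 0% | 25.0 | 64% | 64% | 64% (60/30) |
| 6% | 23.5 | 56% | 60% | 61% (56/28) |
| 12% | 22.0 | 50% | 55% | 59% (53/26) |
| 20% | 20.0 | 43% | 48% | 55% (48/24) |
| 30% | 17.5 | 37% | 41% | 51% (42/21) |

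A fourth case matters. If only new jobs count and employed students gain them at the same 50% and 25%, keeping everyone gives 25 points and 64% at any q, and removing them only costs power.

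**Hyp 6.** Simulated log-rank power (exponential times, censoring at 6 months, 2,000 runs per case) at q = 20% is about 36% under A, 47% under B and 53% under C. At q = 0 it is about 61-62%.

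**Other rates.** With 40% vs 12% (normal approximation), Hyp 5 power is 82% at q = 0. At q = 20% it is 52% (A), 67% (B) and 71% (C).

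**Chance imbalance.** The SD of the arm difference in baseline employment is √[q(1−q)(1/60 + 1/30)]. At q = 20% this is √(0.16 × 0.05) = 0.089, so a difference must reach about 1.96 × 8.9 = 17.5 points to be significant. Under A the risk difference is (0.50 + 0.50·q_VR-M) − (0.25 + 0.75·q_control). An extra 17.5 points in the VR-M arm alone therefore adds 0.50 × 17.5 ≈ 9 points, and in the control arm alone subtracts 0.75 × 17.5 ≈ 13 points. Imbalances just under the threshold would shift a 20-point effect by nearly that much without any adjustment.

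**The case against.** Four objections carry weight.

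**Dilution is not certain.** A reader might infer that students with jobs necessarily shrink the effect. The documents do not support that. Their wording is about attaining a job, which in ordinary use means getting one, and the plan nowhere adopts the reading in which a held job is a success. If only new jobs count, the loss is smaller (treatment B), and it disappears if employed students gain new jobs at the same rates. The risk ratio is also undiluted under B: at q = 20% it is 0.40/0.20 = 2.00, against 0.60/0.40 = 1.50 under A. This stands. The size depends on a coding that the plan leaves open, and that opening is the defect.

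**The share may be small.** Eligible students are still in school or transition programming, and the nearest documented figure is 6-12%. There, removal gains roughly 5 to 9 points of power over treatment A and 1 to 4 over B. This also stands.

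**The workplace site proves nothing.** Section 5.0 C says of one site: "The program is conducted entirely at the workplace where students receive instruction and training in a workplace setting". It is tempting to read this as students holding paid jobs at entry. The text describes instruction and training, so it gives no evidence about baseline employment.

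**The covariate rule is a safeguard.** It would be too strong to say that baseline employment can enter no analysis; the rule could bring it in, and the Cox covariates are not a closed list. But the rule depends on a significance test in about 90 students, and it cannot settle who is at risk or when the event occurs.

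Phase II is also a pilot, with interview skills as the primary target. That limits the weight of the point but does not remove it.

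**Conclusion.** The gap is real. Students with jobs are eligible, their status is surveyed before randomisation, and the Hyp 5 and Hyp 6 analyses do not say what counts as the event, from when time runs, or how these students are handled. Leaving adjustment to a significance test is worse than using a baseline variable that is already collected.

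The size is conditional. It rests on an assumed share with jobs, assumed rates of 50% and 25%, and a coding that the plan does not state. Within those assumptions the power lost relative to removal ranges from about 1 point (6% share, new jobs only) to about 14 points (30% share, held jobs counted as successes). It is negligible when the share is near zero, and there is none if employed students gain new jobs at the same rates. Confidence is high on the omission and low on its size. The change should be made, but the documents do not show that the employment results will be diluted.

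**What to change.** In section 14.0 Data Analysis:

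1. Define the Hyp 5 and Hyp 6 event as the first job started after randomisation, with time counted from randomisation. State what counts as a job.
2. Analyse all randomised students, with baseline employment status as a prespecified covariate (logistic model, Hyp 5) or stratum (log-rank and Cox, Hyp 6), whether or not the arms differ significantly on it.
3. Also report both analyses restricted to students without a job at baseline. That set is defined before randomisation, so the comparison stays randomised, although it answers the question for a narrower population.
4. Name in advance which of the two is the main analysis. Either is defensible.

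The cost is a few lines of text and one extra model term, or fewer students in the restricted set. If no employed student gains a new job, the logistic coefficient for baseline status cannot be estimated. The treatment estimate then equals that from the restricted set, and the plan should say so.

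The fix assumes that the baseline survey records whether the student currently has a job. The protocol gives only its title, so this should be confirmed.

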The PI and or study team will be available to answer any questions the parents may have while reviewing the permission form. After the parents return the form, students under 18 years of age will be approached at school during Study Visit 1 to provide assent. Parents and students will be informed that choosing not to participate will not affect their or the student's relationship with the school or teachers. For students 18 years or older, the research team will send an informational letter home informing the parents of the study and then the research team will approach the students 18-26 years old in order to obtain written informed consent.

Also, teachers from all schools/programs will be recruited to participate in this study as part of an initial implementation. The teachers will be recruited beforehand during a phone call, or through the same educational meeting hosted at the school to inform parents and recruit students.

D.1. Pre-Study Visit:

Parents and teachers will be asked to complete surveys prior to Study Visit 1. Surveys will be administered electronically, or by pen and paper. Completers will receive \$15 (parents and/or teachers).

Parents will be asked to complete:

- 1. Student Background Form and Contact Info Form (age, gender, race, ethnicity, etc.)
- 2. Behavior Checklist (ABCL or CBCL) (Achenbrock & Edelbrock, 2001). These surveys assess behavioral problems and social competencies as reported by parents and/or teachers. They are standardized in the field and have a long history of validity and reliability. If parents do not complete this form, then we will ask the teachers to do so (ABCL/CBCL/TRF).
- 3. Social Responsiveness Scale 2nd Edition (SRS-2) (Constantine & Gruber, 2005), which is a teacher/parent based rating scale that measures the severity of autism spectrum symptoms

Teachers will be asked to complete:

- 1. Teacher Demographic Form
- 2. Social Responsiveness Scale 2nd Edition (SRS-2) (Constantine & Gruber, 2005), which is a teacher/parent based rating scale that measures the severity of autism spectrum symptoms
- 3. Behavior Checklist (ABCL/CBCL/TRF) if parents do not complete the form
- 4. Student Background Form and Contact Info if parents do not complete the form

D.2. Study Visit 1 & 2:

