- B. Quality control We currently have in place a variety of measures to ensure and check the quality of clinical data. All interviewers participate in a formal training course and all clinical data are verified through evaluations by an editor and diagnostician. Data collectors also receive extensive training in the administration of all measures and assessments.
- C. Human Subjects Issues We will use consent language that will clearly stipulate: (1) disclosure that clinical research data will be deposited to this NIH autism database; (2) assurance that such data will be provided without personal identifiers; (3) disclosure that analyses of these data will be conducted by other scientists not included within the current research team; and (4) disclosure that there is no plan to provide subjects with any financial benefits from commercial products derived from the data. All consent materials will be in full accordance with IRBs of participating institutions.

14.0 Data Analysis:

Phase I Data Analysis. The qualitative interview data will be analyzed inductively and iteratively using thematic analysis and the constant comparative approach^{43, 44} to identify emergent themes regarding potential modifications to VR. The research team will analyze a subset of transcripts from the qualitative data to iteratively develop codes until a final codebook is agreed upon by the team and intercoder reliability is achieved; codes will then be applied to transcripts^{45, 46}.

Phase II Data Analysis. For Phase II, between-group differences in the characteristics of the VSU+VR-M and VSU groups will be examined using Chi-Square analysis (categorical variables) or an analysis of variance (ANOVA) (scaled variables). Variables with significant between-group differences will be examined as covariates in all subsequent analyses. Measures of dispersion (mean, standard deviation, variance, range) and distribution (kurtosis, skewness) will be computed. Scatterplots will be generated to review bivariate relationships.

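### Two different models are planned for the pretest-to-posttest outcomes, including the primary target; neither is named as the test of the hypotheses, and baseline significance tests may add covariates

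*Combined protocol and SAP*

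**What the plan says.** Section 1.0 describes Phase II in these words: "To evaluate the feasibility and preliminary effectiveness of VR-M in a randomized pilot trial". Phase IIa makes interview skills the primary target and states Hyp 1-4 as directional between-group claims on interview skills, self-confidence, motivation and anxiety.

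Section 14.0 Data Analysis (Phase II Data Analysis) gives the analysis of these four outcomes:

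- The aim: "We will assess the effect of VR-M on changes in job interview skills, self-confidence, motivation, and anxiety between pretest and postest".
- One model: "We will use repeated-measures ANCOVAs with ASD-related symptoms, depressive symptoms, neurocognitive function, and social cognitive function", entered as covariates.
- A second model, in the next sentence: "We will also use ANCOVA to evaluate the change over time, with posttest scores as the dependent variables while covarying for pretest variables".

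Neither model is linked to a numbered hypothesis or called primary, supportive or sensitivity. The exploratory part of the section assigns bootstrapping to mediators and linear regression to moderators, and does not rank the two ANCOVAs.

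Earlier in the section, the randomised groups are compared at baseline by chi-square tests or ANOVA, with this consequence: "Variables with significant between-group differences will be examined as covariates in all subsequent analyses". No threshold, variable list or retention rule is given.

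**The concern.** The two models treat the pretest differently and carry different covariates. With two occasions, the group-by-time term of a repeated-measures model is a test on change scores, which fixes the pretest slope at 1. Posttest ANCOVA estimates that slope. As listed, the first model has the heterogeneity variables but not pretest as a covariate, and the second has pretest but not the heterogeneity variables.

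Following the plan as written therefore gives two p-values and two intervals for the primary target. If one is significant and the other is not, the document does not say which answers Hyp 1. The baseline-testing rule adds further possible versions of each model, depending on which variables happen to differ between arms.

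**Working it through.** **Inputs.** From the document: n = 90 (section 1.0) and 2:1 allocation (D.4 Randomization), hence 60:30. D.4 also speaks of nearly equal groups, so error rates were checked at 45:45 too. The document gives no alpha, effect size, SD, pre-post correlation or sample-size derivation, so there is no figure to reproduce. Assumed: two-sided 5%; SD 1 at both times; pre-post correlation r = 0.3, 0.5, 0.7; effect 0.6 SD (range 0.4-0.8); no dropout; four covariates; repeated-measures test = change score on arm plus covariates.

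**Precision with the same covariates.** Change-score variance is 2(1 - r). Posttest ANCOVA variance is 1 - r². The ratio of ANCOVA to change score is (1 + r)/2 = 0.65, 0.75, 0.85, with r taken given the covariates. ANCOVA is the more precise.

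**Gap between estimates.** For a chance pretest imbalance of 0.3 SD the two estimates differ by 0.3(1 - r) = 0.21, 0.15, 0.09 SD.

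**Power at 60:30 and 0.6 SD, covariates related equally to pretest and posttest** (20,000 simulated trials per cell; values for r = 0.3 / 0.5 / 0.7):

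| Model | Covariates explain 0% | Covariates explain 30% |
|---|---|---|
| Posttest on arm + pretest | 79 / 86 / 96% | 79 / 86 / 96% |
| Group-by-time with covariates | 59 / 74 / 92% | 59 / 74 / 91% |
| Posttest on arm + pretest + covariates | 77 / 85 / 95% | 87 / 89 / 96% |

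**Disagreement on significance between the two planned models.** At 0.6 SD it is 5-25% (5-26% in a smaller repeat run). At 0.4 SD it is 15-24%, and at 0.8 SD 1-14%. It falls to about 1% at r = 0.8.

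**When covariates relate unequally.** Take r = 0.7 and covariates that explain 20% of posttest variance and none of pretest. Residual variances are:

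- group-by-time with covariates: 2(1 - 0.7) - 0.20 = 0.40
- posttest on pretest only: 1 - 0.49 = 0.51
- posttest on pretest plus covariates: 1 - 0.49 - 0.20 = 0.31

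Here the repeated-measures model beats the planned pretest-only ANCOVA (simulated power 98% v 96%). At 30% explained it is 99.7% v 96%. ANCOVA with pretest plus covariates is still the most precise.

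**False-positive rate if either model could count.** With equal covariate relations it is 7.0-7.7% at 60:30 and 6.8-8.1% at 45:45. A separate run with covariates acting on posttest only through pretest, r up to 0.8, gave 6.3-6.9%. In the unequal case with 30% explained, the null correlation between the two estimates is 0.21/√(0.51 × 0.30) = 0.54, which gives about 9%.

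**Baseline rule.** D.1 and D.2 name roughly ten baseline characteristics. If 5-10 are tested at 5%, the chance of at least one flag under proper randomisation is 1 - 0.95⁵ = 23% to 1 - 0.95¹⁰ = 40% for independent tests, and less if they are correlated. This is the chance of a flag, not an error rate. With the rule applied mechanically to a single model, simulated type I error stayed at 4.5-5.1%.

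**The case against.** The strongest reply is that the text already implies roles. The posttest ANCOVA sentence speaks of change over time, which echoes the stated aim. The repeated-measures sentence follows the moderator discussion and is defined by the heterogeneity variables. On that reading the first is the effect analysis and the second a heterogeneity-adjusted one. This may well be the intent, but the text does not say so: moderators are given to linear regression, and the word "also" sets the two models side by side. The reading reduces the point to a missing label. It does not remove it.

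A reader might infer stronger things that the document does not support:

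- *That the models could give contradictory answers.* They estimate the same effect, and in simulation they were never significant in opposite directions. Disagreement means one significant, the other not.
- *That the repeated-measures model is always the weaker.* This holds with the same covariates in both. As planned, with different covariates, the order depends on how those covariates relate to pretest and posttest.
- *That the trial runs at 6-9% error.* This would require that either result may count, and no section says so.
- *That baseline testing inflates error.* Applied mechanically to one model, it does not materially do so. The wording also says such variables will be examined as covariates, so entry is not automatic.

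The pilot status also stands as a limit on the stakes.

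**Conclusion.** The point holds in moderate form. Section 14.0 gives two non-equivalent analyses of the primary target and of Hyp 2-4, and does not say which one tests them. Under the assumptions above they differ on significance in about 5-26% of trials at 0.6 SD, less when pre-post correlation is high. The baseline rule adds a covariate list that is not settled until the data are seen; the harm there is an open specification rather than a raised error rate. Only n = 90 and 2:1 come from the document, so the percentages are illustrative. The absence of a ranking does not depend on them. A pilot that states directional hypotheses should still say which analysis answers them.

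**What to change.** In section 14.0 Data Analysis, state that Hyp 1 is tested by the arm coefficient, with 95% CI, in an ANCOVA of posttest role-play score on arm and pretest role-play score, and that Hyp 2-4 use the same model with their own pretest and posttest scores. Label the repeated-measures ANCOVA supportive. Make the baseline comparison descriptive, so that it selects no covariates for the deciding models.

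Preferably add a covariate list fixed before outcomes are looked at by arm, drawn from measures already collected: SRS-2, the mood survey and the NIH Toolbox cognition measures, each with its score named. D.1 describes the SRS-2 as an instrument "which is a teacher/parent based rating scale that measures the severity of autism spectrum symptoms", and section E makes teachers the backup for parents, so the informant must be specified. Include social cognitive function only if an existing baseline measure is identified; D.1 and D.2 name none under that label. The pretest-only ANCOVA, already planned, is acceptable if the team prefers it.

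The cost is a few sentences. With added covariates it is also an SRS-2 informant rule, a missing-covariate rule, and about 1-2 points of power if the covariates predict nothing. SRS-2, mood survey and NIH Toolbox need no new data, and the sample size does not change. The team gives up the freedom to choose the model later.
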